## D. RESEARCH DESIGN AND METHODS:

### TRIAL DESIGN:

#### SCHEMATIC SUMMARY OF MEXILETINE TREATMENT IN DM1

This FDA Orphan Product Development Project proposes a double-blind, randomized, placebo-controlled, six month clinical trial of the efficacy and safety of mexiletine (150 mg three times daily) for the treatment of moderately affected ambulatory patients with DM1. Twenty patients will be randomized to receive treatment while another 20 patients will receive placebo. Patients will be randomized in a 1:1 ratio to receive either mexiletine (150 mg three times daily) or placebo. The primary outcome measure will be the assessment of ambulation by six minute walk time. Secondary outcome measures will include: a) grip myotonia as determined by relaxation time following maximum voluntary isometric contraction of the finger flexor muscles; b) muscle strength; c) change in lean muscle mass; d) pain measurement using the Brief Pain Inventory and a

modified Chronic Pain Scale; e) Gastrointestinal function measured by two gastrointestinal questionnaires; f) The ability to swallow as measured by a timed swallowing test with water; g) physical function as measured by the time to rise from a chair, Purdue Peg Board Score, time to walk 30 feet, six minute walk, and SF-36; and, h) pulmonary function (measured by serial determinations of forced vital capacity); i) change in Holter monitor data from baseline; and j) patient relevance as measured by a novel disease-specific health-related quality-of-life instrument designed specifically as an clinical outcome measure for the DM1 population.

During the trial of treatment with mexiletine, all patients will receive careful safety monitoring, including serial EKGs, laboratory testing, three in-person evaluations on the University of Rochester NIH funded Clinical Translational Sciences Institute sponsored Clinical Research Center, and phone calls to assess for any side effects or problems with the study medications, to encourage adherence to the treatment regimen, and to grade musculoskeletal pain. Below is a more detailed description of the study design and the outcome measures.

### **Rationale for Design:**

A randomized, double-blind, placebo-controlled approach was selected based on its efficacy, simplicity, widespread acceptance, and power to compare the efficacy of mexiletine vs. placebo in our study population.

### **Study Population:**

Our decision to select patients with DM1 for our investigation has occurred for several reasons. DM1 is an orphan disease and is appropriate for the Orphan Product Development Grant Program. Published estimates of the prevalence of DM1 in European-American populations range, for example, from 2.4 per 100,000 in Northern Ireland to 5.5 per 100,000 in West Germany. A study from Switzerland, that carefully attempted to obtain complete ascertainment of all cases, has reported a prevalence of 4.9 per 100,000. A general estimate of the prevalence of DM1 in populations Americans is approximately 10 per 100,000 and indicates a total prevalence of less than 100,000 patients with DM in the United States.

In addition, DM1 has clinical and laboratory features that permit careful assessment of symptoms. Patients often have easily identified clinical signs of myotonia, and, as mentioned previously, myotonia may play an important contributory role in their symptoms. For example, myotonia may have an additive effect with weakness to decrease dexterity in performing certain movements with the hands (e.g., compromising employment opportunities). Myotonia may contribute to muscle spasm and pain in the posterior neck and low back (e.g., further compromising employment opportunities). It may hamper swallowing and breathing (e.g., increasing the risk of life threatening illness), and it may worsen already compromised gastrointestinal motility. Myotonia may also exaggerate difficulties with agility, balance, and ambulation caused by progressive weakness (increase the risk of falls and associated injuries).

Demonstration that an effective antimyotonia treatment improves one or more of these clinical problems will provide an opportunity to improve the quality of care of these patients and extend their productive life span.

One of the benefits of studying DM1 patients is that the diagnosis can be definitively established. DM1 is an autosomal dominantly inherited disease and it results from an unstable trinucleotide repeat,  $[CTG]_n$ , expansion in the DM gene on chromosome 19. The gene defect is well characterized and a specific diagnostic test using leukocyte DNA analysis is available to identify the abnormal enlargement of the  $[CTG]_n$  repeat and to identify affected individuals. The availability of a standard diagnostic test for DM1 assures us that all the patients in our study population have a family history DM1.

There will be 40 subjects with myotonic dystrophy between 18-80 years of age enrolled for this clinical trial. Up to 60 patients will be screened for this trial until accrual of 40 patients is met. Every effort will be made to insure that the study population reflects the makeup of the general population, including women and minorities, from which it is drawn.

For over 30 years in our Neuromuscular Disease Center we have provided care to a large population of DM1 patients, and over the past 25 years we have carried out clinical investigations to clarify the pathomechanism of the muscle wasting that occurs in these patients. We have also performed multiple therapeutic trials in subgroups of these DM1 patients. At present we have a funded NIH study to investigate the disease progression of DM1. This study has provided us with access to many patients from our local area and from other regions of the United States. It is possible that these patients may also wish to participate in our therapeutic trial. We also have access to over 580 DM1 patients through the National Registry of Myotonic Dystrophy Patients. We anticipate having no significant difficulty in recruiting the required number of patients for this trial.

### **Patient Selection:**

Myotonic dystrophy type-1 patients of both genders will be recruited for this study. All NIH guidelines regarding gender and minority inclusion will be followed. Issues regarding human subjects are discussed in the section identified as Human Subjects.

All patients must fulfill the following **inclusion criteria** to participate in the study:

- 1) Age 18 years or older and less than or equal to 80 years old.
- 2) Have a diagnosis of myotonic dystrophy type 1 and a 1st degree family member with a positive DNA test for myotonic dystrophy type 1
- 3) Have delayed relaxation of grip of one second or more following a maximum voluntary isometric contraction using our standard Jamar grip ergometer.
- 4) Have sufficient finger flexor strength to grasp the handle of the ergometer used to measure myotonia.
- 5) Have sufficient strength to swallow.

- 6) Be able to walk independently 30 feet and to walk continuously for more than six minutes (cane, walker, orthoses allowed) at a distance over 100 meters.
- 7) Have a reliable method of birth control (if a female subject of child bearing potential).
- 8) Able to swallow an appropriately sized capsule.

Patients with one or more of the following criteria will be **excluded from participation** in the study:

- 1) Known allergy to mexiletine.
- 2) Treatment with mexiletine within past 8 weeks.
- 3) Second or third degree heart block, atrial flutter, atrial fibrillation, ventricular arrhythmias, or is receiving medication for treatment of a cardiac arrhythmia.
- 4) Receiving another antmyotonia drug.
- 5) Liver or kidney disease requiring ongoing treatment.
- 6) Have a seizure disorder.
- 7) Are pregnant or lactating.
- 8) Had severe depression within 3 months of randomization or a history of suicide ideation. Physicians review current medications and clinical assessments of primary care physicians and coordinate participation in the study with them. If the primary care doctor is not comfortable including assessments of cognitive or emotional state (i.e. severe depression) we will not include them in the study until they satisfy all of the inclusion criteria. We always share laboratory data and significant findings with the primary care doctor and any other care providers with permission of the subject.
- 9) History of non-compliance with other therapies.
- 10) Have any one of the following medical conditions: uncontrolled diabetes mellitus, congestive heart failure, symptomatic cardiomyopathy, symptomatic coronary artery disease, cancer other than skin cancer less than five years previously, multiple sclerosis, or other serious medical illness.
- 11) Have any of the following conditions on routine blood screening: WBC <3000, platelets <100,000, hematocrit <30%, symptomatic liver disease, BUN >30mg%.
- 12) Drug or alcohol abuse within 3 months of enrollment.
- 13) Coexistence of another neuromuscular disease.
- 14) Is unable to give informed consent.
- 15) Severe arthritis or other medical condition (besides DM1) that would significantly impact ambulation.

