#### **Baseline Screening:**

A baseline evaluation will determine the eligibility of each recruited individual to participate in the study. At this visit consent will be obtained, and measurements of height, weight, blood pressure, pulse, urinalysis, and electrocardiogram will be performed. A blood specimen will be drawn for: complete blood count and differential

cell count, serum sodium, chloride, potassium, bicarbonate, calcium, phosphorus, total protein, glucose, blood urea nitrogen, prothrombin time, partial thromboplastin time, creatinine, thyroid stimulating hormone, T3, T4, gamma glutamyl transferase, aspartate aminotransferase, and lactic dehydrogenase. A pregnancy test will be given to women of childbearing potential.

Patients will be required to have had a 24 hour Holter monitor study performed within 2 months, or prior to their initial screening visit. The Holter monitoring assessment will occur through collaboration with our study cardiologist, Dr. [REDACTED], who is reviewing the resting electrocardiograms and 24 hour Holter monitoring results on each of the study participants. Patients will come to the University of Rochester Medical Center > 36 hours before their scheduled Clinical Research Center [CRC] visit for out-patient electrode placement and attachment of the Holter recording equipment. The Holter equipment and electrode removal will occur at the time of admission of the participant to the CRC. Rapid review of the tracing will occur to allow a determination of their eligibility after all the initial baseline screening is performed to assure that the patient satisfies the inclusion and exclusion criteria for participation in the trial of mexiletine. The out of town participants will stay in a hotel close to the University of Rochester Medical Center during the period before their CRC admission. The application of the Holter monitor will occur as noted above as an out-patient procedure that will be coordinated through our cardiology group, including Drs. [REDACTED] and [REDACTED] (cardiologists), [REDACTED] (ECG Core Lab Manager) and [REDACTED] (Technician).

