### **Screening Evaluations:**

- Review of the study procedures/consent review: Upon arrival at the CRC, the information in the screening consent form will be reviewed with the patient in detail. The patient will be provided with an opportunity to ask any additional questions prior to starting the study procedures scheduled for the day.
- Standard blood testing. Up to 4 tablespoons of blood will be taken from a vein in the participants arm. This blood will be used for routine laboratory testing listed above and in the schedule. A pregnancy test will also be performed for women of childbearing potential.
- A urine sample will be collected a urinalysis will be performed. Height, weight, and vital signs will be recorded.

- A standard 12 lead electrocardiogram (ECG) test will be performed.
- A study doctor will perform a physical examination and medical history. Medical records will be reviewed.
- A 6-minute walk test (6MWT) will be performed under the supervision of a trained physical therapist. Blood pressure, heart rate, breathing rate, and oxygen saturation will be recorded before and after this test.
- A swallowing evaluation will be conducted to determine the ability of the patient to swallow pills with water.
- Myotonia testing. For this testing we will have the patient grasp a handle that is connected to a computer. The patient will squeeze the handle as strongly as they can for 3 seconds and then relax. The time required for the patient's hand to relax will be recorded by the computer and be used to measure the patient's hand myotonia. To find out if repeated muscle contractions shorten the time required for grip to relax (warm-up effect) a similar test will be performed. With the right hand patients will grasp onto the handle. They will squeeze the handle as strongly as they can for 3 seconds and then relax for 10 seconds. They will repeat this five times. This series of grip exercises will be repeated for a total of 3 sets. Each set will be separated by a 10 minute rest period.

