- Placement of a 12-lead 24-hour Holter monitor test. The patient will come to the University of Rochester Clinical Research Center (CRC) and a technician from the Cardiology Group working on this project will work with the CRC nursing staff to set up the Holter monitor. Patients will not require this testing if they have had a Holter monitor within 2 months. This testing can be done before or after the above screening procedures and after the screening consent form has been reviewed and signed.

**Potential Enrollment: All screening information will be reviewed by the PI to determine subject eligibility. If a patient satisfies all the inclusion and exclusion criteria, the patient will be invited to participate in the research study and a consent form for the treatment trial (attached) will be reviewed with them. If the patient decides to participate in the clinical trial the patient will undergo the following:**

- I. Continuation of the Screening/Baseline Visit at the University of Rochester Clinical Research Center (CRC). This visit will take two days. During this visit a series of evaluations will be carried out to determine how the patient is affected by myotonic dystrophy. An additional aspect of the Screening/Baseline Visit is that the patient will be started and monitored on the study drug (either mexiletine or placebo).

- II. Follow-up visits to the CRC 3 months and 6 months after the Screening/Baseline Visit. During these visits many of the same evaluations from the Screening/Baseline Visit will be repeated to determine how the patient's condition has changed over time.
- III. Telephone evaluations. The patient will receive a telephone call about every two weeks while they are enrolled in the study, except for the weeks when they come to the CRC for a study visit. The study coordinator will telephone the patient to check on any side effects that may occur and make sure that the study medication is being taken as directed. The coordinator will also ask each patient about their pain level during these phone calls.

A schedule of procedures and assessments for this project is outlined in **schedule 1** (Appendix C).

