#### **Description of study procedures:**

The Screening/Baseline Visit of the study will take place over two consecutive days on the CRC. On Day 1 the patient will be admitted to the Clinical Research Center (CRC) for an overnight stay.

Screening/Baseline Visit Day 1 - The activities during the first day will take all day (about 4 hours in the morning and 3 hours in the afternoon). These activities include the screening evaluations listed above as well as the procedures outlined below.

- Review of the study procedures/consent review: Upon arrival at the CRC, the information in the treatment consent form will be reviewed with the patient in detail. The patient will be provided with an opportunity to ask any additional questions they may have prior to starting the study procedures scheduled for the day.
- An assessment of the patient's ability to swallow. A swallowing evaluation will be conducted to determine the time it takes for the patient to swallow water.
- The patient's muscle strength will be tested in several ways by a physical therapist using hand grading and a myometer. The patient's force vital capacity will be checked. The patient will be timed as they get up from a chair and walk 30 feet and perform a Purdue Peg Board test and Jebsen-Taylor Hand function tests. The patient will be asked to pinch a piece of equipment with their fingers to measure their pinch strength.
- Each patient will be given a standard lunch on the CRC.
- They will be asked to complete a series of questionnaires to find out how myotonic dystrophy impacts upon the patient's life and daily activities. These include the following questionnaires: Upper Extremity Functional Index, myotonia visual analog scale, Medical Outcome Short Form Health Survey (SF 36), Epworth Sleepiness Scale, an Individualized Neuromuscular Quality of Life

Questionnaire (INQoL), two gastrointestinal function questionnaires, a chronic pain scale and brief pain inventories, and a DM1 specific Health related quality of life questionnaire (MDHI). Additionally, patients will be asked to complete an assessment of the usability and relevance of some of these questionnaires (i.e., SF-36, INQoL, and MDHI).

- Each patient will receive a standard dinner on the CRC.
- After all of the baseline assessments are completed, each patient will receive the first dose of study medication (mexiletine or placebo) with dinner. The patient will stay overnight on the CRC.

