	n; m+sd or freq.	n; m+sd or freq.	n; m+sd or freq.
12-lead ECG			
Heart rate bpm			
R-R interval sec.			
PR interval sec.			
QRS duration sec.			
QT interval sec.			
QTc interval sec.			
T-wave amplitude in Lead II mm			
2nd degree block y/n			
3rd degree block y/n			
Other ECG abn y/n			
24-hour Holter			
VPB frequency #/hr			
VPB pairing y/n			
VPB triplets y/n			
VPBc $\geq$ 4 but <10 in a row y/n			
Ventricular tachyarrhythmia >10 in a row y/n			
rate bpm			
2nd degree block y/n			
3rd degree block y/n			
Sinus pause/arrest >3 sec y/n			
Symptoms/Signs			
Syncope y/n			
Chest pain y/n			
Palpitations y/n			
Possible adverse Mexiletine effects y/n			

Our DSMB will be organized to help monitor these data and will include a cardiologist (Dr. [REDACTED]), a biostatistician (Dr. [REDACTED]), and a neurologist (Dr. [REDACTED]) with DSMB experience. None of the members of the DSMB have active collaborations with the investigators on this grant and none are members of the specific subspecialty units of which the investigators are faculty members.

The criteria for DSMB intervention will consist of three levels:

**Level One-** Abnormality noted. Possible normal variation. Clinically non-significant.

**Level Two-** Abnormality noted. Potential clinical significance. Requires further review and decision by DSMB.

**Level Three-** Critical Value. Clinically significant and immediate intervention required.

Any Level Three occurrence will warrant a temporary stoppage of study medication use for an individual patient until an expedited DSMB determination can be made.

Figure 3 below lists possible observable cardiac findings via ECG or Holter monitoring and each event's required DSMB action.

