**Figure 3: Required DSMB interventions for possible cardiac events.**

Data Category	Variable	DSMB Intervention Level
ECG	1 degree AV block	1
ECG	2 nd Type 1	2
ECG	2 nd type 2	3
ECG	3 rd degree AV block	3
ECG	Sinus tachycardia	1
ECG	Sinus bradycardia	2
ECG	New Bundle branch block	2
ECG	QRS widening>50%	3
ECG	QTc>500msec	3
Holter Monitoring	PVC frequency Increase	2
Holter Monitoring	Nonsustained VT Increase	2
Holter Monitoring	Sustained VT	3
Clinical Symptom	Syncope/unresponsiveness	3

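### No QTc limit at entry, although an absolute QTc above 500 msec on study is a Level 3 critical value that stops study drug

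*Combined protocol and SAP*

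**What the plan says.** **At entry.** Exclusion criterion 3 under Patient Selection lists "Second or third degree heart block, atrial flutter, atrial fibrillation, ventricular arrhythmias, or is receiving medication for treatment of a cardiac arrhythmia". Criterion 10 adds heart failure, symptomatic cardiomyopathy, symptomatic coronary disease and a general clause for other serious illness. Criterion 11 sets numeric limits for white cells, platelets, hematocrit and BUN. None of the 8 inclusion or 15 exclusion criteria gives a limit for any ECG interval.

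**At screening.** The screening list includes the ECG: "A standard 12 lead electrocardiogram (ECG) test will be performed". The Baseline Screening section has the study cardiologist "reviewing the resting electrocardiograms and 24 hour Holter monitoring results on each of the study participants", and the enrolment paragraph states "All screening information will be reviewed by the PI to determine subject eligibility". Baseline Screening also says that a patient who meets the inclusion criteria and no exclusion criterion is enrolled. Under Randomization, the coordinator verifies the eligibility criteria before calling the pharmacy.

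**Dosing.** On Day 1, once baseline assessments are complete, "each patient will receive the first dose of study medication (mexiletine or placebo) with dinner". Day 2 lists doses with breakfast and lunch, and then an ECG read by a physician in real time.

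**On study.** Figure 3 assigns Level 3 to a QTc above 500 msec. The section on cardiac conduction defects defines Level Three as "Critical Value. Clinically significant and immediate intervention required" and says that any such occurrence warrants a "temporary stoppage of study medication use for an individual patient until an expedited DSMB determination can be made".

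**The concern.** A value that the plan treats as critical once a patient is on drug should not be an acceptable value for starting the drug. The QTc row is absolute: it does not ask whether the interval has lengthened. A patient with a long but stable QTc therefore meets the stop rule at the first on-treatment ECG without any drug effect.

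Two things are at stake. The patient takes study drug, possibly an antiarrhythmic, at a QTc that the plan says calls for immediate action. The DSMB is then asked for an expedited decision, with treatment interrupted, over a finding that was visible before the first dose.

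**Working it through.** No power, alpha or event figure is involved, so the check sets the entry criteria against the on-study action levels.

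**Step 1: the Level 3 rows.** Figure 3 has 13 rows, of which 6 are Level 3. For each, can it already be present at screening without meeting a named exclusion?

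| Level 3 row | Status at entry |
|---|---|
| Second-degree block, type 2 | Barred by criterion 3 |
| Third-degree block | Barred by criterion 3 |
| Sustained VT | Barred by criterion 3 (ventricular arrhythmias) |
| "QRS widening>50" per cent | A change from an earlier tracing, so cannot be present at baseline |
| Syncope or unresponsiveness | A clinical event on study, not an ECG value |
| QTc above 500 msec | No matching criterion: open |

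The count is 3 barred + 1 relative + 1 clinical event + 1 open = 6. QTc is the only ECG or Holter item left open.

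**Step 2: is the QTc row meant as a change?** Its wording gives no sign of that. The QRS row is a widening, and the bundle branch block row (Level 2) applies only to a new block. The plan thus separates new from pre-existing findings in two rows and does not do so for QTc.

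**Step 3: follow one patient with a stable QTc of 510 msec (illustrative).**

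1. The screening ECG shows 510 msec. No listed criterion is met.
2. Baseline Screening directs enrolment, and the coordinator's eligibility check finds nothing to stop it.
3. The first dose is given with dinner on Day 1.
4. Doses two and three are listed with breakfast and lunch on Day 2, ahead of the Day 2 ECG. In the mexiletine arm that is up to 3 × 150 mg = 450 mg, if the listed order is the clock order.
5. The Day 2 ECG again shows 510 msec. Since 510 > 500, the Level 3 rule applies: drug is stopped and the DSMB is called.

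**Step 4: how often?** The documents give no QTc distribution or rate for DM1. The Preliminary Studies section shows that patients with first-degree block and bundle branch block took part in the earlier crossover trials, under criteria stated to be identical. Baseline conduction disease is therefore to be expected, but those are different findings and give no QTc frequency.

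**Step 5: cost of closing the gap.** The Study Population section allows up to 60 screened for 40 enrolled, so 60 − 40 = 20 screen failures. If the new clause removed one or two more patients (assumption), that would use 1/20 = 5% to 2/20 = 10% of the allowance.

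**The case against.** The strongest reply is that expert review already guards entry. A cardiologist reads every resting ECG and Holter, the PI reviews all screening data before the treatment consent, and the general clause in criterion 10 could be invoked. For the gap to matter, both would have to see a QTc above the study's own critical value and proceed. This makes the event less likely, and it is why the point is about what the written rules permit. It does not close the gap: no QTc value is given for either review, and the enrolment text directs entry when no criterion is met.

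It can also be argued that the plan reaches baseline values. The Figure 2 template has a baseline column with a QTc row, seen by the DSMB with abnormal values highlighted, and Figure 3 is not limited to post-dose tracings. But nothing makes the same-evening first dose wait for that review, and the Level 3 action is to stop a drug, which presupposes that dosing has begun.

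Several objections stand as limits on the size of the point:

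- No frequency can be shown.
- The documents do not say that mexiletine lengthens QTc or is hazardous at a long baseline QTc.
- The patient stays overnight on the research unit and the Day 2 ECG is read in real time, so undetected exposure should be brief.
- The two earlier trials, of 20 patients each, are reported as completed without significant adverse events.
- A cut-off at 500 msec still admits a patient at 498 msec, who could cross the line through measurement variation alone.
- Schedule 1 and the Manual of Operations are not in the text reviewed, so a handling rule there cannot be ruled out. The eligibility list itself is complete, and an exclusion belongs in it.

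**Conclusion.** The concern holds. The entry criteria contain no QTc limit, while an absolute QTc above 500 msec is a Level 3 value that stops drug. As written, a patient already above that value at screening can be randomised, dosed and then stopped with no change in the ECG.

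The size is modest: brief exposure (up to 450 mg in the mexiletine arm on the listed order of events) and one avoidable expedited DSMB review for each such patient. The number of such patients is unknown. No effect on sample size, power, Type I error or the primary estimate is claimed. The conclusion rests on reading the QTc row as absolute, as it is worded, and on discretionary review not having intervened. The change should be made because it is nearly free and bears on patient safety.

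**What to change.** **Preferred.** Add to exclusion criterion 3 a QTc above 500 msec on the screening 12-lead ECG. The study cardiologist should name the correction formula and say how QTc is judged when bundle branch block is present. If the cardiologist wants a margin for measurement variation near the threshold, a lower entry limit can be chosen at the same time.

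**Alternative.** Reword the QTc row of Figure 3 relative to the screening ECG, in line with the QRS and bundle branch block rows. This prevents a stop with no change but still admits a patient at the critical value, so the exclusion is the safer choice.

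**Cost.** One clause, or one reworded table row. No new test is needed, since the screening ECG is already done before the first dose. The downside is possibly one or two more screen failures (assumption) out of the 20 allowed.
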